3.6.2.3. Severity of Adverse Events

“Severity” of the AE refers to the extent to which an AE affects the subject’s daily activities and differs from “Serious,” which is a regulatory classification.

The Investigator is to classify the severity of an AE according to the following definitions:

- **Mild:** The symptom has a negligible effect or no impairing effect on the subject’s normal function.
- **Moderate:** The symptom impairs the subject’s normal function to some extent.
- **Severe:** The symptom has an obvious, significantly impairing effect on the subject’s normal function.

3.6.2.4. Relationship of Adverse Events to Study Treatments

The Investigator is to classify the drug relationship of an AE according to the definitions outlined in [Table 6](#).

Table 6: Relationship of AE to Study Drug

| Association | Definition |
|-------------|--|
| Not related | (1) the existence of a clear alternative explanation (e.g., mechanical bleeding at surgical site) or (2) non-plausibility, e.g., the subject is struck by an automobile or cancer developing a few days after drug administration. |
| Unlikely | There is no medical evidence to suggest that the AE may be related to study drug usage, or there is another more probable medical explanation. |
| Possible | There is medical evidence to suggest that there is a reasonable possibility that the AE may be related to study drug usage. However, other medical explanations cannot be excluded as a possible cause. |
| Probable | There is strong medical evidence to suggest that the AE is related to study drug usage. |
| Definite | A clinical event, including laboratory test abnormality (if applicable), in which there is no uncertainty in its relationship to test drug (e.g., positive Rechallenge). |

3.6.3. Reporting Adverse Events

Adverse events that occur from first dose through completion of the last study visit should be reported. All SAEs, regardless of causality, occurring from the time of informed consent until 30 days following study completion OR until 30 days after the subject's last application of study medication, whichever is longer, must be reported to TKL Clinical Safety within 24 hours of the knowledge of the occurrence (this refers to any adverse event that meets any of the aforementioned serious criteria). SAEs occurring after the 30-day follow-up period AND considered related to study drug must also be reported to the Sponsor.

Every attempt should be made to describe the AE in terms of a diagnosis. If a clear diagnosis has been made, individual signs and symptoms will not be recorded unless they represent atypical or extreme manifestations of the diagnosis, in which case they should be reported as separate events. If a clear diagnosis cannot be established, each sign and symptom must be recorded individually.

Any SAEs occurring in a subject receiving study drug must be reported to the Sponsor within 24 hours of the site being informed of the event, even if the event does not appear to be drug-related. The report must be made by sending a completed SAE Report form to the Sponsor. Any pertinent follow-up information should be provided in a similar manner. Contact information is provided in [Section 3.7.1](#).

3.6.4. Adverse Event Follow-up

Any ongoing AE at the time of study completion or withdrawal will be followed until the AE is resolved or the subject is referred to his/her own PMD. The Investigator and the Sponsor will decide if longer follow-up is appropriate on a case-by-case basis. Subjects who experience any clinically significant AE will remain under medical supervision until the Investigator or the Sponsor's Medical Monitor deems the AE to be resolved, stabilized, or no longer serious enough to warrant follow-up.

3.6.5. Pregnancy reporting

Prior to study enrollment, females of childbearing potential must be advised of the importance of avoiding pregnancy during study participation and the potential risk factors for an unintentional pregnancy. The signed Informed Consent Form must document this discussion.

A UPT will be performed on all females of childbearing potential at Day 1 (day of first patch application) and EOS. All women of childbearing potential will receive a UPT prior to the first study drug administration and the study drug must be withheld until the results of laboratory pregnancy testing are available. If pregnancy is confirmed, the subject must not receive any study drug and must not be enrolled in the study.

3.6.6. Expected Adverse Events

Any observed response in the patch test area that can be denoted using the irritation criteria summarized in [Table 3](#) and [Table 4](#) will not be considered an AE.

Tape related reactions will only be recorded as AEs when the subject is discontinued due to tape reaction around all sites. When 1 or 2 sites are experiencing severe tape related reactions, the application site will be stopped and the subject will continue on the study. This will be noted in the database as "T" as indicated in [Table 5](#) and will be considered an expected AE. When all application sites are experiencing tape reaction, the subject is discontinued and therefore be recorded as an AE. The subject will be followed up through resolution.

3.7.2. Reporting Responsibility

Any death, SAE, pregnancy, (see [Section 3.6](#)), or unusual frequency of AEs, must be reported immediately (i.e., not later than 24 hours after first learning of its occurrence) to the Sponsor's study manager by the Investigator, even if the event(s) appear to be unrelated to study treatment. Follow-up information about a previously reported SAE or pregnancy must also be reported to the Sponsor within 24 hours of receiving it. If the SAE or pregnancy has not been previously documented (i.e., is a new occurrence) and it is thought to be related to the investigational product (or therapy), the Sponsor may contact the Investigator to obtain further information. If warranted, an investigator alert may be issued, to inform all Investigators involved in any study with the same product (or therapy) that this SAE or pregnancy has been reported.

The IRB should also be notified of SAEs or pregnancies and of any follow-up information in writing, as is practical, and depending on local regulations.

3.7.3. Reporting procedures

For each SAE, the Investigator will complete a SAE Report Form in English and assess the relationship of each SAE to study treatment. The completed form(s) should be sent by e-mail to the Sponsor within 24 hours of first knowledge of the SAE (as outlined in [Section 3.7.1](#) and [Section 3.7.2](#)). The initial SAE should be reported immediately, even if only preliminary information is available. Follow-up information should be sent by the same Investigator, restating the date of the original report. Either a new SAE form is sent (stating that it is a follow-up), or the original one is resent (with the new information highlighted and a new date provided). The follow-up should describe whether the event has resolved or continues, if and how it was treated, whether the blind was broken or not, and whether the patient continued or discontinued study participation. The form confirmation will be retained.

Pregnancy follow-up (as outlined in [Section 3.6.5](#)) should be reported to the IRB within 24 hours of first knowledge on a Pregnancy Report Form. Follow up will describe the outcome of the pregnancy, including any voluntary or spontaneous termination, details of the birth, and the presence or absence of any congenital abnormalities or birth defects.

3.8. Appropriateness of Safety Measurements

The safety assessments in the study are standard safety measures in clinical trials.

4. STATISTICAL METHODS

4.1. General Considerations for Data Analysis

The RIPT study design using 200 subjects is considered adequate to identify any significant safety hazard due to the potential of a topically administered dermatologic agent to induce allergic sensitization. Individual subjects' cutaneous responses after Challenge Phase are classified as indicative of sensitization or not indicative of sensitization based on specific criteria defined in terms of an ordinal rating scale. The occurrence in this study of even a single reaction indicative of sensitization is sufficient to suggest that the test product may have the potential to cause hypersensitivity.

The statistical analyses described below will be supplemented by a comprehensive Statistical Analysis Plan (SAP) which will be finalized before the database is locked. Any changes to the statistical plans will be described and justified in the final report.

All statistical processing will be performed using the SAS® system (version 9.2 or higher). No interim or subgroup analyses are planned.

4.2. Sample Size and Power Considerations

The sample size of 200 evaluable subjects conforms to industry and regulatory standards for determination of dermal sensitization potential. In the absence of any sensitization reactions, a 95% upper confidence bound on the population rate of sensitization would be 1.5%.

4.3. Subject Populations for Analysis

All subjects who receive treatment will be evaluable for AEs. The evaluation of sensitization will be based on all subjects who complete the Challenge Phase of the study. The analysis of cumulative irritancy will be based on all subjects who complete the Induction Phase of the study.

4.3.1. Background and Demographic Characteristics

Descriptive statistics will be used to summarize demographic characteristics (age, gender, Fitzpatrick skin type, and race) and background characteristics for the randomized subject population. Past/coexistent medical history information for all randomized subjects will be presented in a by-subject listing.

4.3.2. Study Product/Visit Compliance

Descriptive statistics will be used to summarize study product compliance for the randomized subject population.

4.4. Prior and Concomitant Medications

Prior and concomitant medication information for all randomized subjects will be presented in a by-subject listing.

4.5. Efficacy Evaluation

This section is not applicable to this study.

4.6. Safety Evaluation

4.6.1. Cumulative Irritancy

Cumulative irritancy during Induction will be quantified by means of the cumulative irritancy index (CII), defined as the mean of the total cumulative irritation scores received during the Induction Phase (9 readings). The total cumulative irritation score for each subject and product will be calculated by summing each individual's scores on each of the 9 evaluation days in the Induction Phase. Response grades will be assigned numerical scores according to [Table 3](#) and [Table 4](#). Once the maximum score (combined score from [Table 3](#) and [Table 4](#)) or a 3 or greater is achieved, the remaining scores of 3 will be carried forward through all subsequent readings. No data imputations are to be made for discontinued subjects or missed evaluations.

The CII will be tested pairwise for product differences using Fisher's protected least significant differences in the context of the 2-way analysis of variance (ANOVA) including main effects of subject and product, without interaction. Pairwise differences will be tested for all products at the 5% level. Mean cumulative irritation scores will also be presented for each patch in a listing.

4.6.2. Analysis of Dermal Sensitization Potential

The determination of dermal sensitization potential will be based on specific scoring criteria ([Table 3](#)) derived from observations in the Challenge Phase of the study and confirmed in the Rechallenge Phase, if necessary.

Criteria specified in [Section 3.5.5](#) may cause the continuation of a subject into the Rechallenge Phase of the study. The recurrence of a cutaneous response of 3 or greater from [Table 3](#) at Rechallenge equivalent to or more severe than that observed at Challenge will be considered indicative of a sensitization reaction. The observation of such a response in even a single subject suggests that the test product may have the potential to cause hypersensitivity.

A narrative description of reactions in the Challenge and Rechallenge Phases will be provided together with the opinion of the Investigator as to whether such reactions are felt to be indicative of contact sensitization.

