3.2. Discussion of Design

Allergic contact dermatitis (ACD), also referred to as dermal sensitization, is a delayed-type hypersensitivity reaction induced by small reactive chemicals (haptens).² It is a T-cell-mediated skin inflammatory systemic reaction, caused by repeated skin exposure to contact allergens. Erythema, edema, and occasionally papules and vesicles characterize the clinical appearance of this reaction. The ACD inflammatory skin reaction occurs as a delayed response (24-48 hours or longer) after contact with a sensitizing chemical.

In pharmaceutical and cosmetic industries it is mandatory to identify chemicals that are potential ACD inducers before they become a part of a new product.² Substances that come into contact with human skin need to be evaluated for their propensity to irritate and/or sensitize. Once an appropriate pre-clinical safety evaluation has been performed, a reproducible, standardized, quantitative patch evaluation procedure must be used to demonstrate that a particular material can be applied safely to human skin without significant risk of adverse reactions.³

Repeated insult patch test (RIPT) evaluation is a predictive patch study that can detect weak sensitizers that require multiple applications to induce a T-cell-mediated (Type IV) immune response sufficient to cause an allergic reaction. Irritant reactions may also be detected using this evaluation method, although this is not the primary purpose of this procedure.

The human RIPT study design is based on the Modified Draize procedure, and is an accepted standard methodology used for assessment of skin sensitization.^{4,5}

The IPs in the study will be CCP-020 (Diacerein 1%) topical ointment and Vehicle. The negative irritant control field will be 0.9% saline, 0.2 mL, applied topically under occlusive conditions.

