test sites on Wednesday, Thursday, Friday, and Saturday), using the procedures described above for the Induction Phase. A possible follow-up reading may be conducted at 96 (± 4) hours for subjects with a score of 3 or higher at the 72 (± 4) hour time point.

Concomitant medications and AEs will be reviewed and recorded at the time of evaluation.

To be considered a **completed case**, a subject must have 9 applications of the study material and no fewer than 8 subsequent readings during Induction Phase and one application followed by 4 subsequent readings during the Challenge Phase. Only completed cases will be used to assess sensitization.

Rechallenge

A subject will be rechallenged to a specific study material if, in the opinion of the Investigator, any sign suggestive of contact sensitization (definite erythema with papules and/or edema) is observed at any of the 4 Challenge evaluations or at the Investigator's discretion for that study material.

Rechallenge patches will be applied at least 2 weeks after the end of the Challenge Phase. The study material will be applied to naïve sites on the back, in a manner similar to that used in the Challenge Phase. Rechallenge patches will remain in place for 48 (± 1) hour and patch sites will be evaluated 30 (+ 10) minutes and 24 (± 1), 48 (± 1), and 72 (± 4) hours after removal. As an example, patches will be applied on Monday and removed on Wednesday; the test sites will be evaluated on Wednesday, Thursday, Friday, and the following Saturday.

End of Study

At the EOS, all patches will be removed as described above, and the final evaluations of the test sites will be made.

An EOS examination will be conducted and consist of the following:

- Concomitant medication
- AEs
- UPT in females of childbearing potential

Concomitant medications and AEs will be reviewed and recorded during the whole study. For a detailed listing of scheduled study time points refer to the Visit Schedule and Assessments ([Table 2](#)).

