3.5.5. Safety Assessments

3.5.5.1. Local Tolerability Assessments

Assessment of the patch sites will be conducted by a trained evaluator once at Baseline (Day 1), 9 times during the Induction Phase, 4 times during the Challenge Phase and, if applicable, 4 times during Rechallenge. The trained evaluator will assign a grade to each site ([Table 3](#)). There will be a main evaluator for the study; a backup evaluator will also be assigned in the event that an emergency occurs and the main evaluator is unable to attend the study visit. For the purpose of statistical analysis only, each grade will correspond to a score. The following symbols and their respective numerical equivalents (see [Table 3](#)) will be used to express the response observed at the time of examination (see [Table 4](#)):

Table 3: Response Symbols and Numerical Equivalents

| Grade | Score* | Definition |
|--------------|---------------|---|
| 0 | 0 | No evidence of irritation |
| 1 | 1 | Minimal erythema; barely perceptible |
| 2 | 2 | Definite erythema, readily visible; or minimal edema; or minimal papular response |
| 3 | 3 | Erythema and papules |
| 4 | 3 | Definite edema |
| 5 | 3 | Erythema, edema, and papules |
| 6 | 3 | Vesicular eruption |
| 7 | 3 | Strong reaction spreading beyond test site |

*Scores are utilized only during the statistical analysis process of the study. Grades will be conducted throughout the study by the trained evaluator.

Table 4: Effects on Superficial Layers of Skin

| Grade | Score* | Response |
|-------|--------|--|
| A | 0 | Slight glazed appearance |
| C | 1 | Marked glazing |
| E | 2 | Glazing with peeling and cracking |
| F | 3 | Glazing with fissures |
| G | 3 | Film of dried serous exudate covering all or portion of the patch site |
| H | 3 | Small petechial erosions and/or scabs |

*Scores are utilized only during the statistical analysis process of the study. Grades will be conducted throughout the study by the trained evaluator.

Other notations (see [Table 5](#)) may be made in place of a score to designate particular circumstances preventing the assignment of a score or in addition to a score to identify damage to the epidermis and/or spreading of a reaction beyond the patch site.

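### Does Section 4.6.2 need to name the Table 3 column and the readings on which Rechallenge is compared with Challenge?

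*Combined protocol and SAP*

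**What the plan says.** Section 4.6.2 sets the formal criterion. A Table 3 response of 3 or more must recur "at Rechallenge equivalent to or more severe than that observed at Challenge will be considered indicative of a sensitization reaction". It then adds: "The observation of such a response in even a single subject suggests that the test product may have the potential to cause hypersensitivity". The same section requires a narrative of Challenge and Rechallenge reactions, with the Investigator's opinion on sensitization.

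Section 3.5.1 schedules the readings:

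- Challenge is read at 30 minutes and at 24, 48 and 72 hours after patch removal. In addition, "A possible follow-up reading may be conducted at 96 (± 4) hours for subjects with a score of 3 or higher" at the 72-hour reading.
- For Rechallenge, "patch sites will be evaluated 30 (+ 10) minutes and 24 (± 1), 48 (± 1), and 72 (± 4) hours after removal". No 96-hour reading is mentioned.
- Rechallenge is triggered when a suggestive sign "is observed at any of the 4 Challenge evaluations", or at the Investigator's discretion.

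Section 3.5.5.1 gives the number of site assessments as "4 times during the Challenge Phase and, if applicable, 4 times during Rechallenge". Its Table 3 has a grade column from 0 to 7 and a score column from 0 to 3, in which grades 3 to 7 all score 3. The table footnote says: "Scores are utilized only during the statistical analysis process of the study".

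Section 3.1 states the Rechallenge trigger as a grade. It also bases the interpretation of contact sensitization on Table 3 grading at Challenge together with the pattern seen during Induction.

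**The concern.** The criterion serves the primary objective, and one subject can decide whether it is met. A reader of Section 4.6.2 alone meets two open choices.

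The first is the column. That section speaks of scoring criteria and sits under Statistical Methods, and the Table 3 footnote assigns scores to statistical analysis. On scores, every response from grade 3 to grade 7 is equal, so the severity clause could never exclude a recurrence.

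The second is the set of readings. Challenge can have five and Rechallenge has four. If the highest grade in each phase is compared, a reaction that peaks only at 96 hours raises the Challenge side with nothing to match it at Rechallenge. Two identical reactions could then be classified differently because the optional reading was taken in one subject and not in the other. The extra reading is offered only for reactions still at 3 or more at 72 hours. Section 3.2 says that allergic contact dermatitis "occurs as a delayed response (24-48 hours or longer) after contact with a sensitizing chemical", so late reactions appear to be the ones of interest.

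**Working it through.** **The plan's own figure.** Section 4.2 gives a 95% upper bound of 1.5% for 0 reactions in 200 subjects. The exact one-sided bound is 1 − 0.05^(1/200) = 1.49%, and the rule of three gives 3/200 = 1.5%. The figure is reproduced. If one subject changed class, the bound for 1 in 200 solves (1 − p)^200 + 200p(1 − p)^199 = 0.05, which gives p = 2.35%. That is the most a single disputed classification would move this bound.

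**Conventions assumed here, not stated in the protocol.** More severe means a numerically higher Table 3 grade. A score of 3 or higher at 72 hours means a Table 3 grade of 3 to 7.

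**Effect of the column.** Take pairs of highest grades, each from 3 to 7: 5 × 5 = 25 pairs. On grades, Rechallenge is lower in 4 + 3 + 2 + 1 + 0 = 10 pairs, so 15 meet the criterion. On scores both sides equal 3, so all 25 meet it. The threshold of 3 selects the same Table 3 responses in either column; only the severity clause depends on the choice.

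**Effect of the 96-hour reading.** Let m be the highest Challenge grade at the four shared readings (3 to 7) and g the 96-hour grade (0 to 7): 5 × 8 = 40 combinations. Let Rechallenge repeat Challenge at all four shared readings, so its highest grade is m.

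| Comparison | Missed when | Combinations missed |
|---|---|---|
| Highest grade, 96 hours included | g > m | 4 + 3 + 2 + 1 + 0 = 10 of 40 |
| Highest grade, four shared readings | m < m | 0 of 40 |
| Same-time grades (96 hours has no partner) | never | 0 of 40 |
| Scores | 3 < 3 | 0 of 40 |

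Example: Challenge 2, 3, 3, 3, then 5 at 96 hours; Rechallenge 2, 3, 3, 3. With 96 hours included the comparison is 3 against 5 and the criterion is missed. On the four shared readings it is 3 against 3 and the criterion is met.

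**Direction.** The extra reading can only raise the Challenge side if highest grades are compared. If last readings were compared, a Challenge reaction at 5 at 72 hours and 3 at 96 hours would have its comparator lowered from 5 to 3. A Rechallenge grade of 4 at 72 hours would then meet the criterion (4 against 3), where it would miss it without the extra reading (4 against 5). So the one-sided effect belongs to one assumed rule.

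**What the rest of the protocol settles.**

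- *Column.* Section 3.1 ties the interpretation itself, and not just the trigger, to Table 3 grading. Section 4.6.2 specifies no statistical test for which scores would be needed. Because scores stop at 3, both the words allowing a response above 3 and the severity clause have effect only on grades.
- *Readings.* Challenge is counted as four readings three times: in the completed-case definition and the Rechallenge trigger in Section 3.5.1, and in the assessment count in Section 3.5.5.1. The 96-hour reading is an optional follow-up outside all three counts, and nothing brings it into the comparison.
- *Timing.* The delay in Section 3.2 runs from contact. The patch stays on for 48 hours, so the 72-hour reading is already 48 + 72 = 120 hours after contact began, and the 96-hour reading is 144 hours after. The four shared readings extend well past the 24 to 48 hours named there, although that wording is open-ended.

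**The case for a change.** The strongest case for a change is that no sentence limits the comparison in Section 4.6.2 to four readings. The counts of four elsewhere serve the trigger, the completed-case definition and the assessment schedule. Its cross-reference for Rechallenge criteria does not help: it points to Section 3.5.5, which supplies the scale, while the triggers stand in Sections 3.1 and 3.5.1. Section 4.1 describes a two-way classification, indicative or not indicative, so a missed criterion might be read as a negative. No rule covers a formal result that differs from the Investigator's opinion, or a Challenge responder without Rechallenge data. Writing the definition down would cost two or three sentences.

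It stands that the text is silent, and that the 10 of 40 and 10 of 25 counts are right under their conventions. It does not stand that the plan as written gives a wrong classification. To reach one, the analyst must choose highest grades and also add an optional reading to a set that the protocol repeatedly counts as four. The reaction must then peak at 96 hours, above every earlier grade. Even so, Section 4.6.2 makes the criterion a sufficient sign of sensitization and does not call a reaction that misses it negative. That reaction is still narrated with the Investigator's opinion, and the planned conclusion is itself worded as a possibility. Divergence between opinion and criterion is conceivable, but nothing in the protocol shows that it is likely. The choice between highest-grade and same-time comparison is partly preference, since both remove the mismatch.

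**Conclusion.** No change to the plan is needed. Section 4.6.2 omits a detail that the rest of the protocol lets an analyst supply: Table 3 grades, over the four readings that both phases share. Under that reading 0 of 40 combinations are affected. The 10 of 40 arises only if highest grades are compared with the optional 96-hour reading included, and it counts listed combinations without any weight for how often they occur. The mix of score and grade wording is loose but does not move the threshold of 3.

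This rests on three assumptions: that the severity clause is meant to have effect, which points to grades; that the 96-hour reading is follow-up outside the four counted Challenge readings; and that the Investigator's narrative is reported as planned. The comprehensive SAP that Section 4.1 promises before database lock is not in the supplied text. It is the ordinary place for such a definition, and its absence here is not evidence that the definition is lacking.

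### A Challenge reactor without a complete Rechallenge stays in the sensitization denominator but has no assigned class, and on the only scored criterion defaults to not indicative

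*Combined protocol and SAP*

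**What the plan says.** **Criterion.** Section 4.6.2 bases the determination on Table 3 scores "derived from observations in the Challenge Phase of the study and confirmed in the Rechallenge Phase, if necessary". The one scored rule that follows is that a response of 3 or more recurring "at Rechallenge equivalent to or more severe than that observed at Challenge will be considered indicative of a sensitization reaction". The same section, like the Synopsis and Section 3.1, also calls for a narrative of Challenge and Rechallenge reactions with the Investigator's opinion on whether they indicate contact sensitization.

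**Analysis set.** Section 3.5.1 defines a completed case by 9 Induction applications with at least 8 readings, plus "one application followed by 4 subsequent readings during the Challenge Phase. Only completed cases will be used to assess sensitization". Section 4.3 uses all subjects who complete Challenge. Neither requires Rechallenge.

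**Timing.** Section 3.5.1: "Rechallenge patches will be applied at least 2 weeks after the end of the Challenge Phase". Four readings are planned.

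**Classes and decision rule.** Section 4.1 sorts each subject's response into one of two classes, indicative or not, by criteria on an ordinal scale. It adds: "The occurrence in this study of even a single reaction indicative of sensitization is sufficient to suggest" that the product may cause hypersensitivity. Section 4.6.2 repeats this.

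**Precision.** Section 4.2: "In the absence of any sensitization reactions, a 95% upper confidence bound on the population rate of sensitization would be 1.5" per cent.

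**Missing data.** The only sentence on missing evaluations is in Section 4.6.1 and concerns cumulative irritancy.

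**The concern.** The rule for a positive needs data that the analysis set does not require. A subject can react at Challenge, count as a completed case, and have no Rechallenge reading on which a recurrence could be scored. Nothing in the sensitization section says how to classify that subject, and there is no indeterminate class.

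Such subjects are foreseeable. Rechallenge comes at least two weeks after Challenge and re-exposes someone who has just reacted. Section 3.3.3 allows refusal at any time, and Section 3.3.4 lists withdrawal and loss to follow-up. Section 3.3.3 also provides for ending further patching of a product after a grade 3 or greater reaction at any point in the study, while Sections 3.1 and 3.5.1 call for Rechallenge after such reactions. Read literally, the protocol itself can produce a reactor who is not rechallenged.

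The missing data concern exactly the subjects who carry the information. In a study that a single case can decide, the scored rule and the analysis set together push that missingness towards a finding of no sensitization.

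**Working it through.** **1. Follow one subject through the text.** Take a subject with 9 Induction applications, enough Induction readings, all 4 Challenge readings, a grade of 3 or more to CCP-020 at Challenge, and no Rechallenge.
- Sections 3.5.1 and 4.3: in the analysed set.
- Section 4.6.2, scored rule: a recurrence at Rechallenge is required; none can be observed; not met.
- Section 4.1: two classes only, so on the scored rule the subject lands in *not indicative*.
- Section 4.6.2, narrative: the Investigator may still call the Challenge reaction indicative. No scoring rule governs this, and the text does not say whether the opinion enters the count.

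A partly missed Rechallenge differs only if a recurrence shows at a reading that was made. The scored rule is then met.

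**2. Reproduce the plan's figure.** Inputs from Section 4.2: n = 200, no reactions, 95% upper bound.
- Exact, one-sided: 1 − 0.05^(1/200) = 1.487%, which rounds to 1.5%.
- Rule of three: 3/200 = 1.500%.
- Exact, two-sided: 1 − 0.025^(1/200) = 1.83%.

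The stated figure is therefore a one-sided bound, although Section 4.2 does not say so.

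**3. Classify the subject in each possible way.** For one case, the exact one-sided bound U solves (1 − U)^200 + 200·U·(1 − U)^199 = 0.05.

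| Treatment of one such subject | Count | One-sided 95% upper bound | Single-reaction rule met? |
|---|---|---|---|
| Not indicative | 0/200 | 1.49% | No |
| Removed | 0/199 | 1.49% | No |
| Counted | 1/200 | 2.35% | Yes |

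With two such subjects the bounds are 1.49% (0/200), 1.50% (0/198) and 3.11% (2/200). Classification drives the result; the loss of a subject or two from the denominator hardly matters.

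**4. Effect on the chance of detection.** The documents give no rate of missed Rechallenge, so the following is conditional. Let p be the true rate and r the assumed fraction of true reactors who complete Rechallenge, with the rest not counted. Then P(at least one counted case) = 1 − (1 − p·r)^200.

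| True rate p | r = 1 | r = 0.8 | r = 0.5 |
|---|---|---|---|
| 1% | 1 − 0.990^200 = 86.6% | 1 − 0.992^200 = 79.9% | 1 − 0.995^200 = 63.3% |

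At p = 1.5%, the rate that the plan's bound refers to, the chance is 1 − 0.985^200 = 95.1% for r = 1 and 1 − 0.9925^200 = 77.8% for r = 0.5.

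**The case against.** The strongest reply is that Section 4.6.2 states a sufficient condition, not a necessary one. A recurrence at Rechallenge makes a positive; the text does not say that nothing else can. The determination starts from Challenge, confirmation is needed only where necessary, and the Investigator gives an opinion on Challenge reactions too. This stands. A reader might infer that Rechallenge recurrence is the only route to a positive, or that the plan counts an unretested reactor as negative. The documents support neither: recurrence is the only *scored* route, and no text assigns the negative class. What remains is that the other route has no criteria, that its bearing on the count is unstated, and that the text never says when Challenge alone suffices.

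Second, Section 4.1 promises a fuller SAP before database lock. That text is not in the document reviewed and may contain the rule. If so, a cross-reference closes the point.

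Third, the magnitude is conditional. Step 3 requires that such a subject occurs, and every r in step 4 is assumed. It is tempting to add that the strongest reactors are the least likely to return, but the documents give no evidence for that. The 1.5% figure is also a planning statement; Section 4.6.2 does not itself plan a bound.

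Fourth, Section 3.2 notes that irritant reactions may also be detected. Counting every unretested reaction as sensitization would blur that distinction. This is a good reason to show two counts rather than fold these subjects into one.

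**Conclusion.** The point holds in this form. The only scored criterion requires Rechallenge and the analysis set does not. A Challenge reactor without a complete Rechallenge and without a recorded recurrence therefore has no pre-specified class and, on the scored criterion alone, defaults to *not indicative*. The Investigator's opinion can override that default, but only by unscored judgement on the subject who may decide the study.

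One such subject separates 0/200 (bound 1.49%) from 1/200 (2.35%) and decides whether the single-reaction rule is met. Even then the stated consequence is that the product may have the potential to sensitize, not that it has been shown to. The fall in detection at a true rate of 1%, from 86.6% to 79.9% or 63.3%, rests on assumed completion of 80% or 50% and on all non-completers going uncounted. The plan's 1.5% is correct as a one-sided bound for zero reactions; what is unsettled is which subjects may contribute to the zero.

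**What to change.** In Section 4.6.2 and the SAP, before database lock:

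1. Define an *unconfirmed Challenge reactor*, by product, as a completed case who met the Rechallenge trigger (grade 3 or higher, or Investigator discretion, as Section 3.1 reads), has one or more Rechallenge readings missing (including all of them), and shows no qualifying recurrence at any available reading. A qualifying recurrence at any available reading counts as confirmed, so the two classes do not overlap.
2. Do not classify unconfirmed reactors as *not indicative*. Give them their own row, by product, with the numbers who triggered and who completed Rechallenge.
3. Report the single-reaction conclusion and the exact one-sided 95% bound twice: for confirmed cases only, and for confirmed plus unconfirmed cases. State that no sensitization was seen only if both counts are zero.

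The cost is some wording, a table row and a second bound; no visit or procedure changes. The downside is that an irritant reaction never retested may make the reported figure less favourable; showing both counts makes that visible.

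Separately, the provision in Section 3.3.3 on ending further patching after a grade 3 or greater reaction at any point in the study must be reconciled with the Rechallenge provisions in Sections 3.1 and 3.5.1.
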